8.3.4.1. Pregnancy Testing

A serum pregnancy test will be required for all WOCBP during screening. Urine pregnancy tests will be performed locally, as outlined in the SoA (see [Table 3](#)), and as medically indicated (eg, in case of loss of menstrual cycle or when pregnancy is suspected).

If a urine pregnancy test is positive, the results must be confirmed with a serum pregnancy test. If the serum pregnancy test is negative after a urine test was positive, the investigator will assess the potential benefit/risk to the participant and determine whether it is in the participant's best interest to resume study drug and continue participation in the study.

If a pregnancy is confirmed by a serum pregnancy test, see [Section 9.8](#) for reporting requirements.

8.3.4.2. Serology

HIV and hepatitis screening assessment will be performed at the screening visit (see [Table 3](#) and [Table 8](#)). Generally, virology and serology tests should be performed early in the screening process due to the length of time needed to obtain the results. Additional tests may be performed if clinically indicated.

8.6. Unscheduled Visits

Unscheduled visits may occur at any time medically warranted, including when participants develop new areas of LP. Any assessments performed at those visits should be recorded in the eCRF.

8.7. End of Treatment and Early Termination

The EOT coincides with the Week 32 visit. A participant that completes the Week 32/EOT2 visit will have reached the EOT with study drug.

If a decision is made that the participant will permanently discontinue study drug prior to the Week 32/EOT2 visit, then the ET visit should be conducted. If the ET visit coincides with a regular study visit, then the ET evaluations will supersede those of that scheduled visit, and the data should be entered in the ET page in the eCRF. If this decision does not coincide with a regular visit, reasonable efforts should be made to have the participant return to the site to complete the ET procedures.

8.8. Follow-Up

8.8.1. Safety Follow-Up

The safety follow-up period is the interval between the Week 32 (EOT2)/ET visit and the scheduled follow-up visit, which should occur 30 days (+ 7 days' visit window) after the Week 32 (EOT2)/ET visit (or 30 days after the last application of study drug if the Week 32 (EOT2)/ET visit was not performed). Participants who have been in an observation/no treatment cycle from Week 28 or earlier until Week 32 do not need to complete the safety follow-up visit.

Adverse events and SAEs must be reported up until 1) at least 30 days after the last application of study drug or 2) until toxicities resolve, return to baseline, or are deemed irreversible, whichever is longer. Reasonable efforts should be made to have the participant return for the follow-up visit and report any AEs that may occur during this period.

9. ADVERSE EVENTS: DEFINITIONS AND PROCEDURES FOR RECORDING, EVALUATING, FOLLOW-UP, AND REPORTING

9.1. Definition of Adverse Event

Adverse Event Definition

• An AE is any untoward medical occurrence associated with the use of a drug in humans, whether or not it is considered drug-related.• An AE can therefore be any unfavorable or unintended sign (including an abnormal laboratory finding), symptom, or disease (new or exacerbated) temporally associated with the use of study drug.
Additional Guidance for Events Meeting the Adverse Event Definition

• Any safety assessments (eg, ECG or vital signs measurements), including those that worsen from baseline, considered clinically significant in the medical and scientific judgment of the investigator (ie, not related to progression of underlying disease) are to be reported as an AE.• Abnormal laboratory test results are to be reported as an AE if they are considered clinically meaningful, induce clinical signs or symptoms, require concomitant therapy, or require changes in study drug. Whenever possible, a diagnosis (eg, anemia or thrombocytopenia) should be recorded in the eCRF rather than the abnormal laboratory test result (eg, low hemoglobin or platelet count decreased).• Exacerbation of a chronic or intermittent pre-existing condition/disease, including either an increase in the frequency and/or intensity of the condition, is to be reported as an AE.• New conditions detected or diagnosed after the start of study drug administration are to be reported as an AE.• Signs, symptoms, or the clinical sequelae of a suspected drug-drug interaction are to be reported as an AE.• Signs and/or symptoms from dose administration errors of a study drug (eg, overdose) or a concomitant medication are to be reported as an AE.• "Lack of efficacy," "disease progression," or "failure of expected pharmacological action" will not be reported as an AE or SAE. Such instances will be captured in the efficacy assessments. However, the signs, symptoms, and/or clinical sequelae resulting from lack of efficacy will be reported as an AE or SAE if they fulfill the definition of an AE or SAE.• A condition that leads to a medical or surgical procedure (eg, endoscopy or appendectomy) will be reported as an AE if it occurs after obtaining informed consent. If the condition is present before entering the study, then it should be captured as medical history.• Pre-existing diseases or conditions with expected fluctuations in signs or symptoms should be reported as an AE only if the investigator judges the fluctuation to have worsened more than expected during study participation.

9.2. Definition of Serious Adverse Event

If an event is not an AE per the definition above, then it cannot be an SAE even if serious conditions are met (eg, hospitalization for signs/symptoms of the disease under study, death due to progression of disease).

A serious adverse event is defined as any untoward medical occurrence that, at any dose:	
a. Results in death	
b. Is life-threatening	
The term "life-threatening" in the definition of "serious" refers to an adverse drug experience that places the participant, in the opinion of the initial reporter, at immediate risk of death from the adverse experience as it occurs. This does not include an adverse drug experience that, had it occurred in a more severe form, might have caused death.

c. Requires inpatient hospitalization or prolongation of existing hospitalization	
In general, hospitalization signifies that the participant has been detained (involving at least an overnight stay) at the hospital or emergency department for observation and/or treatment that would not have been appropriate in the physician's office or outpatient setting. Complications that occur during hospitalization are AEs. If a complication prolongs hospitalization or fulfills any other serious criteria, the event is serious. When in doubt as to whether hospitalization occurred or was necessary, the AE should be considered serious.
 
Hospitalization for elective treatment or planned surgery (eg, stent replacement, hip surgery) is not considered an SAE.
 
Hospitalization for medical interventions in which no unfavorable medical occurrence occurred (ie, elective procedures or routine medical visits) is not considered an SAE.

d. Results in persistent or significant disability/incapacity	
The term "disability" means a substantial disruption of a person's ability to conduct normal life functions. This definition is not intended to include experiences of relatively minor medical significance, such as uncomplicated headache, nausea, vomiting, diarrhea, influenza, and accidental trauma (eg, sprained ankle), that may interfere with or prevent everyday life functions but do not constitute a substantial disruption.

e. Is a congenital anomaly/birth defect	
f. Is an important medical event	
An important medical event is an event that may not result in death, be immediately life-threatening, or require hospitalization but may be considered serious when, based on appropriate medical judgment, the event may jeopardize the participant and may require medical or surgical intervention to prevent one of the outcomes listed in the above definition. Examples of such events include new invasive or malignant cancers; intensive treatment in an emergency department or at home for allergic bronchospasm, blood dyscrasias, or convulsions that do not result in hospitalization; development of drug dependency or drug abuse; or suspected transmission of an infectious agent via a medicinal product.

9.3. Recording and Follow-Up of Adverse Events and/or Serious Adverse Events

Adverse Event and Serious Adverse Event Recording

- An AE/SAE that begins or worsens after informed consent is signed should be recorded on the Adverse Events Form in the eCRF. All AEs/SAEs should be reported for enrolled participants, but only SAEs need to be reported for screen failure participants. For enrolled participants, conditions that were present at the time informed consent was given should be recorded on the Medical History Form in the eCRF. For detailed information, refer to the eCRF guidelines.
- When an AE/SAE occurs, it is the responsibility of the investigator to review all documentation (eg, hospital progress notes, laboratory reports, or diagnostic reports) related to the event.
- The investigator (or delegate) will then record all relevant AE/SAE information in the eCRF.
- It is **not** acceptable for the investigator to send photocopies of the participant's medical records in lieu of completing the Adverse Events Form in the eCRF.
- There may be rare instances when copies of medical records for certain cases are requested. In this case, all participant identifiers, with the exception of the participant ID number, will be redacted by the site staff on the copies of the medical records before submission. These records can be submitted to Incyte Pharmacovigilance by email/fax per the contact information listed as per SAE completing guidelines.
- The investigator will attempt to establish a diagnosis of the event based on signs, symptoms, and/or other clinical information. Whenever possible, the diagnosis (not the individual signs/symptoms) will be documented as the AE/SAE. When a clear diagnosis cannot be identified, each sign or symptom should be reported as a separate AE/SAE.

To the extent possible, each AE/SAE should be evaluated to determine the following:

- The severity grade (CTCAE v5.0 Grades 1 to 5). See below for further instructions on the assessment of intensity.
- Whether there is at least a reasonable possibility that the AE is related to the study drug: suspected (yes) or not suspected (no). See below for further instructions on the assessment of causality.
- The start and end dates, unless unresolved at the final safety follow-up visit.
- The action taken with regard to study drug as a result of the AE/SAE(s).
- The event outcome (eg, not recovered/not resolved, recovered/resolved, recovering/resolving, recovered/resolved with sequelae, fatal, or unknown).
- The seriousness, per the SAE definition provided in Section 9.2.
- The action taken with regard to the event. Note: If an AE is treated with a concomitant medication or nondrug therapy, this action should be recorded on the Adverse Events Form and the treatment should be specified on the appropriate eCRF (eg, Prior/Concomitant Medications, Procedures and Non-Drug Therapy).

Assessment of Intensity

The severity of AEs will be assessed using CTCAE v5.0 Grades 1 through 5. If an event is not classified by CTCAE, the severity of the AE will be graded according to the scale below to estimate the grade of severity.

The investigator will make an assessment of intensity for each AE and SAE reported during the study and assign it to 1 of the following categories:

- **Grade 1:** Mild; asymptomatic or mild symptoms; clinical or diagnostic observations only; treatment not indicated.
- **Grade 2:** Moderate; minimal, local, or noninvasive treatment indicated; limiting age-appropriate activities of daily living.
- **Grade 3:** Severe or medically significant but not immediately life-threatening; hospitalization or prolongation of hospitalization indicated; disabling; limiting self-care activities of daily living.
- **Grade 4:** Life-threatening consequences; urgent treatment indicated.
- **Grade 5:** Fatal.

Assessment of Causality

- The investigator is obligated to assess the relationship between study drug and each occurrence of each AE/SAE.
- A "reasonable possibility" of a relationship conveys that there are medical facts, evidence, and/or arguments to suggest a causal relationship, rather than that a relationship cannot be ruled out.
- The investigator will use clinical judgment to determine the possibility of a relationship.
- The investigator will also consult the RSI in the **IB** in making their assessment.
- Alternative causes, such as underlying or concurrent disease(s), concomitant therapy, and other risk factors, as well as the temporal relationship of the event to study drug administration, will be considered and investigated.
- For each AE/SAE, the investigator **must** document in the medical notes that they have reviewed the AE/SAE and have provided an assessment of causality.
- With regard to assessing causality of SAEs:
 - There may be situations in which an SAE has occurred and the investigator has minimal information to include in the initial report. However, the causality assessment is one of the criteria used when determining regulatory reporting requirements. **Therefore, it is very important that the investigator always make an assessment of causality based on the available information for every event before the initial transmission of the SAE.**
 - The investigator may change their opinion of causality in light of follow-up information and submit the updated causality assessment.

Follow-Up of Adverse Events and Serious Adverse Events

- The investigator is obligated to perform or arrange for the conduct of supplemental measurements and/or evaluations as medically indicated or as requested by the sponsor to elucidate the nature and/or causality of the AE or SAE as fully as possible. This may include additional laboratory tests or investigations, histopathological examinations, or consultation with other health care professionals.

- Once an AE is detected, it should be followed in the Adverse Events Form in the eCRF until it has resolved or until it is judged to be permanent; assessment should be made at each visit (or more frequently if necessary) of any changes in severity, the suspected relationship to the study drug, the interventions required to treat the event, and the outcome.
- When the severity of an AE changes over time for a reporting period (eg, between visits), each change in severity will be reported as a separate AE.
- If a participant dies during participation in the study or during a recognized follow-up period, the investigator will provide the sponsor with a copy of any postmortem findings, including histopathology.
- Updated SAE information will be recorded in the originally completed eCRF and reported to Incyte Pharmacovigilance (either via email/fax if paper SAE form is used or in the SAE EDC CRF) until resolution, stabilization, the event is otherwise explained, or the participant is lost to follow-up.
- Any updated SAE data (including SAEs being downgraded to nonserious) will be submitted to the sponsor (or designee) within 24 hours of receipt of the information.

9.4. Reporting of Serious Adverse Events

Regardless of suspected causality (eg, relationship to study drug or study procedure[s]), all SAEs occurring after the participant has signed the ICF through the last study visit or at least 30 days after the last application of study drug must be reported to the sponsor (or designee) immediately, without undue delay but not later than within **24 hours** of obtaining knowledge of its occurrence unless otherwise specified by the Protocol. The investigator will submit any updated SAE data to the sponsor (or designee) immediately, without undue delay but not later than within 24 hours of it being available.

Investigators are not obligated to actively seek SAE information after the safety follow-up visit or more than 30 days after the last dose of study drug. If the investigator learns of any SAE, including death, at any time during this period, and they consider the event to be reasonably related to the study drug or study participation, then the investigator must notify the sponsor (or designee) within 24 hours of becoming aware of the event.

After the initial AE/SAE report, the investigator is required to proactively follow each participant at subsequent visits/contacts. All SAEs will be followed until resolution, stabilization, the event is otherwise explained, or the participant is lost to follow-up (as defined in Section 7.3).

Prompt notification by the investigator to the sponsor regarding an SAE is essential so that legal obligations and ethical responsibilities toward the safety of participants and the safety of a study drug under clinical investigation are met.

If the SAE is not documented in the RSI of the **IB** (new occurrence) and is thought to be related to the study drug, the sponsor or its designee may urgently require further information from the investigator for expedited reporting to health authorities. The sponsor or its designee may need to issue an Investigator Notification to inform all investigators involved in any study with the same drug that this SAE has been reported. Suspected unexpected serious adverse reactions will be collected and reported to the competent authorities and relevant ethics committees in accordance with Directive 2001/20/EC or per national regulatory requirements in participating countries.

The sponsor has a legal responsibility to notify both the local regulatory authority and other regulatory agencies about the safety of a study drug under clinical investigation. The sponsor

will comply with country-specific regulatory requirements relating to safety reporting to the regulatory authority, IRB/IEC, and investigators.

Investigator safety reports must be prepared for suspected unexpected serious adverse reactions according to local regulatory requirements and sponsor policy and forwarded to investigators as necessary.

An investigator who receives an investigator safety report describing an SAE or other specific safety information (eg, summary or listing of SAEs) from the sponsor will review and then file it along with the IB and will notify the IRB/IEC, if appropriate, according to local requirements.

Serious Adverse Event Reporting

- Information about all SAEs is collected and recorded on the Adverse Events Form in the eCRF.
- The investigator must report within 24 hours of learning of its occurrence, any SAE via the EDC system (primary method) or by completing the Serious Adverse Event Report Form in English (only if the EDC system is not available). The contact information for Incyte Pharmacovigilance by email/fax is listed in the Study Reference Manual or the Incyte Reference Guide for Completing the Serious Adverse Event Report Form.
- In circumstances where the EDC system is not accessible for reporting SAE information (initial and/or follow-up SAE information) to the sponsor within 24 hours, refer to the Incyte Reference Guide for Completing the Serious Adverse Event Report Form. Once the EDC system is functional, the SAE report should be retrospectively added to the EDC system and follow-up should be completed through the EDC. The original copy of the Serious Adverse Event Report Form and the email or facsimile confirmation sheet must be kept at the study site (refer to the Incyte Reference Guide for Completing the Serious Adverse Event Report Form or Study Reference Manual for details and for the email address or fax number).
- Follow-up information is also recorded in the eCRF and transmitted to Incyte Pharmacovigilance via the EDC system. The follow-up report should include information that was not provided previously, such as the outcome of the event, treatment provided, action taken with study drug because of the SAE (eg, dose reduced, interrupted, or discontinued), or participant disposition (eg, continued or withdrew from study participation). Each recurrence, complication, or progression of the original event should be reported as follow-up to that event, regardless of when it occurs.

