9.2. Adverse Events

9.2.1. Adverse Event Definitions

A TEAE is any AE either reported for the first time or worsening of a pre-existing event after first application of study drug and within 30 days of the last application of study drug. For participants who cross over treatments, the first application date is period-specific; however, the end date is 30 days after the last application date in this period, or the first application date in the next period, whichever comes first. Analysis of AEs (as discussed below) will be limited to TEAEs, but data listings will include all AEs regardless of their timing in relation to study drug application.

Adverse events will be tabulated by MedDRA PT and SOC. Severity of AEs will be graded using the NCI CTCAE v5. The CTCAE reporting guidelines and grading details are available on the Cancer Therapy Evaluation Program website.

The subset of AEs considered by the investigator to be related to study drug will be considered to be treatment-related AEs. If the investigator does not specify the relationship of the AE to study drug, the AE will be considered to be treatment-related. The incidence of AEs and treatment-related AEs will be tabulated. In addition, serious TEAEs will also be tabulated.

Any missing onset date, causality, or severity must be queried for resolution. Unresolved missing causality and severity will be handled according to the following rules:

- An unresolved missing causality will be considered treatment-related.
- An unresolved missing severity will be identified as an unknown severity.

For purposes of analysis, all AEs will be considered TEAEs unless the AE can unequivocally be defined as not treatment-emergent.

Application site reactions are AEs that occur at the site of drug application. A summary of ASRs will be provided.

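### Protocol 9.4 files serious recurrences as follow-up to the original event with no time limit, which conflicts with Protocol 9.2, 9.3 and SAP 9.2.1 and can leave a same-grade recurrence on ruxolitinib uncounted in that period

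*Protocol*

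**What the plan says.** Protocol 9.4, in the block on SAE reporting, states: "Each recurrence, complication, or progression of the original event should be reported as follow-up to that event, regardless of when it occurs". It sets no time limit, and makes no exception for an event that has resolved or for a participant whose treatment has changed.

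The rule reaches the clinical database as well as the sponsor's safety file. Section 9.4 says "Information about all SAEs is collected and recorded on the Adverse Events Form in the eCRF" and "Follow-up information is also recorded in the eCRF and transmitted to Incyte Pharmacovigilance via the EDC system". Section 9.3 adds "Updated SAE information will be recorded in the originally completed eCRF".

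Other provisions point a different way:

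- Protocol 9.2 treats complications arising in hospital as adverse events, and says "If a complication prolongs hospitalization or fulfills any other serious criteria, the event is serious".
- Protocol 9.3 says that when severity changes over a reporting period, "each change in severity will be reported as a separate AE".
- SAP 9.2.1 defines a treatment-emergent adverse event (TEAE) by its timing against study drug application. It says "For participants who cross over treatments, the first application date is period-specific", and it closes each window 30 days after the period's last application or at the first application of the next period, whichever is earlier.
- SAP Appendix A plans separate adverse event tables for the double-blind vehicle-controlled (DBVC) period, the open-label extension (OLE), and both combined.

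**The concern.** Allocating events to periods by date works only if each episode has its own date. Vehicle participants who continue into the OLE cross over to ruxolitinib, so for them the period decides whether an event counts under vehicle or under active drug. If a serious event resolves on vehicle, recurs on ruxolitinib and is entered only as follow-up to the first record, the database may hold no event dated in the ruxolitinib period. SAEs are also reportable from consent under Protocol 9.4. A serious event before Day 1 that recurs on treatment raises the same question, with no TEAE window covering the only recorded onset.

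Safety and tolerability is a stated secondary objective, and few SAEs can be expected in a trial of about 60. A serious event that returns after active drug is started is one a safety reader would want to see in the period where it happened. Because 9.2, 9.3 and 9.4 give different instructions for complications and progressions, sites could also record like events differently.

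**Working it through.** The plan gives no figure on this point, so there is nothing to reproduce. The check applies the SAP 9.2.1 windows to example records.

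**Inputs**

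- Period lengths: 16 weeks each (Protocol 4.1). Assumed full timeline for a vehicle participant: vehicle on Days 1 to 16 × 7 = 112, ruxolitinib on Days 113 to 32 × 7 = 224.
- Window rule: SAP 9.2.1.
- Vehicle arm: about 60 / 2 = 30 (Protocol 10.1). The number who cross over is not given; 30, 25 and 20 are assumptions.

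**Windows**

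- DBVC: opens on Day 1 and closes at the earlier of 112 + 30 = Day 142 and the first OLE application on Day 113, so it closes at Day 113.
- OLE: opens on Day 113 and closes at 224 + 30 = Day 254.

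**Example records, classified on onset date alone**

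| Record in the database | In DBVC window | In OLE window |
|---|---|---|
| Original SAE, onset Day 60 on vehicle | yes | no |
| Recurrence with its own record, onset Day 150 | no | yes |
| Original SAE, onset Day -10 (before first dose) | no | no |

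If the Day 150 recurrence exists only as follow-up to the Day 60 record, the first row is all the tables can use, and the participant counts under vehicle only. If the only record is dated Day -10, a recurrence after Day 1 falls in neither window on onset date. It is then a TEAE only if the SAP's worsening clause or its default rule is applied.

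**Which events are exposed**

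- Change in severity: 9.3 calls for a separate event, so a recurrence or progression at a different grade should have its own record. A lower grade is also a change, but if the first episode has ended it is unclear whether 9.3 or 9.4 governs.
- Complication in hospital: 9.2 makes it an adverse event.
- Complication with a new diagnosis: 9.1 requires new conditions found after the start of study drug to be reported as adverse events.
- Same diagnosis, same or lower grade, after resolution: only 9.4 addresses this directly, and it says follow-up.

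**Illustrative size**

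One participant missing from the vehicle-to-ruxolitinib OLE column shifts the serious TEAE rate by 1/n:

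- n = 30: 1/30 = 3.3% (exact 95% CI 0.1% to 17.2%) against 0/30 = 0% (0% to 11.6%)
- n = 25: 1/25 = 4.0% (0.1% to 20.4%) against 0/25 = 0% (0% to 13.7%)
- n = 20: 1/20 = 5.0 points

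**The case against.** The strongest reply is that neither document says a recurrence keeps the earlier onset date or is left out of a table. The 9.3 sentence on updating the original record runs only until resolution or stabilization, so it does not clearly govern a later episode. The 9.4 sentence sits among reporting instructions and can be read as linking cases for the sponsor. Recording belongs to 9.3, which requires start and end dates for each event and defers detail to eCRF guidelines that are not part of these documents. All of this stands. A reader might infer that every recurrence, complication or progression on ruxolitinib necessarily drops out of the ruxolitinib tables. The documents do not support that.

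The reply is also right on scope. Sections 9.1, 9.2 and 9.3 already capture most complications and progressions. The SAP counts worsening of a pre-existing event as a TEAE, and counts any event as a TEAE unless it unequivocally is not. A vehicle-onset SAE stays in the DBVC and combined-period tables and in the listings, so it would be misattributed but not lost. Where the first episode was itself on ruxolitinib, follow-up under that record leaves it attributed to ruxolitinib. For that reason the remark in Protocol 6.5.1 about recurrence on restarting drug does not show a misattribution. With two or fewer participants the SAP may replace a table with a listing, and nothing here touches the primary endpoint.

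These points do not close the gap. The inclusion default helps less when the only recorded onset plainly precedes the window, and it does not create a second record for the OLE table. Nor do the documents tell a site which of 9.2, 9.3 and 9.4 prevails.

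**Conclusion.** The point holds as a conflict between passages with a narrow consequence. Protocol 9.4 is inconsistent with 9.2 and 9.3, and it does not supply the episode-level onset that SAP 9.2.1 relies on. Followed literally, it can leave a serious event that resolves and recurs, with the same diagnosis at the same or lower grade, without a record in the period of recurrence. For a vehicle participant who crosses over, the event could then appear only under vehicle, in the combined table and in listings. For a pre-dose SAE, it could appear only in listings unless the worsening or default rule is applied.

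Such events will be rare, and the documents give no SAE or recurrence rate from which to estimate a frequency. The shift of 3.3 points with 30 crossovers (4.0 with 25, 5.0 with 20) is the effect of one assumed event, not a forecast. It also rests on the assumption that a follow-up entry carries no onset date of its own, which the eCRF guidelines could confirm or remove. The point is worth correcting because a stated rule, and not just missing detail, creates the risk, and because the correction is small.

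**What to change.** Limit the 9.4 sentence to further information on the same ongoing episode. Suggested content: further information on an ongoing episode is reported as follow-up; a recurrence after resolution, or a complication with its own diagnosis, is recorded as a new AE or SAE with its own onset date and linked to the original event; worsening is recorded as 9.3 already requires. Then align 9.2, 9.3, 9.4 and the eCRF completion guideline, so that SAP 9.2.1 works on the onset of each episode.

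This costs one protocol sentence and a matching line in the eCRF guideline. The downside is an occasional extra linked SAE record to reconcile with the safety database. It changes record-keeping only and leaves clinical management as it is.
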